In the diagnosis of RPOC, clinical practice usually combines the patient's history of delivery or miscarriage, symptoms of persistent or recurrent vaginal bleeding, serum β -HCG level, and transvaginal/abdominal Doppler ultrasound showing heterogeneous masses in the uterus to make a definitive diagnosis. The sensitivity of transvaginal Doppler ultrasound can reach 94%, and the specificity can reach 98% ^[2], so it is widely used in the diagnosis of retained products of pregnancy. As a supplementary means of ultrasound, pelvic MRI has more characteristic features and can clearly show the anatomical structure of the uterus, assess the relationship between the placenta and the myometrium, and clarify the location and depth of implantation, which is of great significance for the diagnosis and differentiation of RPOC ^[3].

The short-term complications of RPOC include vaginal bleeding and infection, while the long-term complications include intrauterine adhesions and infertility ^[4]. A study by Ben - Ami I proposed that retained products of conception are an independent risk factor for infertility ^[5].

In terms of the treatment of retained products of pregnancy, the main clinical treatment methods are divided into surgical treatment and non-surgical treatment. Non-

surgical treatment mainly includes expectant management and drug treatment. A retrospective cohort study by Wada Yoshimitsu ^[6] included 54 patients with RPOC, of whom 44 patients chose expectant management. 34 patients (77%) had their retained pregnancy tissue expelled spontaneously without intervention and did not require surgical treatment. The other 10 patients (23%) underwent hysteroscopic surgery for "persistent vaginal bleeding" and concluded that expectant management is effective and can reduce the number of intrauterine operations. Zeng Wenjuan ^[7] et al. found that although the vaginal bleeding time was longer after expectant management than after curettage, no serious hemorrhage occurred. They also suggested that expectant management is equally safe and effective compared with curettage and can replace some curettage treatment. However, expectant management has a long follow-up time and requires high patient compliance. A meta-analysis by Li Mengxi ^[8] believed that expectant management is an effective treatment method and that patients with retained products of pregnancy <50mm in diameter and stable vital signs are suitable for expectant management. However, there is a difference in the effectiveness of expectant management compared to surgical management. Patients who undergo curettage can completely expel the remaining pregnancy tissues through surgery in a short period of time, so curettage is considered to be a more effective treatment method. In fact, clinicians are usually worried that the continued presence of pregnancy tissues in the uterus may lead to serious complications such as bleeding or infection. Therefore, they tend to actively treat the disease to reduce the incidence of complications. However, some studies have shown that there is no statistically significant difference in the risk of patients needing emergency curettage for massive bleeding, whether they undergo expectant management or curettage. On the contrary, curettage may increase the risk of postoperative infection ^[8]. With repeated intrauterine operations, the incidence of intrauterine adhesions gradually increases. Intrauterine adhesions seriously affect menstrual recovery and subsequent pregnancy, and have become an important cause of infertility. Some studies have reported that the incidence of intrauterine adhesions after curettage is about 29.6%, and the incidence of intrauterine adhesions in patients who undergo curettage again after incomplete abortion due to pregnancy tissue residue can increase to 40%, of which 75% are moderate to severe intrauterine adhesions ^[9]. 83.1% of patients with severe intrauterine adhesions had related curettage for pregnancy ^[10]. In fact, the incidence of intrauterine adhesions may be more than that. Since the typical clinical manifestation of intrauterine adhesions is reduced menstrual flow, and severe cases are accompanied by secondary infertility, it mainly affects the patient's fertility, but has no significant impact on daily life. Therefore, some patients do not seek medical attention or receive related treatment. Therefore, for patients who want to have children, expectant management is a good choice to reduce the number of intrauterine procedures, prevent the occurrence of intrauterine adhesions, and protect the patient's fertility.

Studies have reported that adding sequential estrogen-progesterone therapy to expectant management can improve the effectiveness of expectant management, shorten the duration of vaginal bleeding, and reduce the amount of bleeding. The success rate of this treatment is 66.7-96% ^[11-14]. The principle is mainly that estrogen promotes endometrial proliferation and repair, which loosens the remnants from the

basal layer, while progesterone can cause stroma atrophy, promote the formation of cervical mucus plug, and reduce intrauterine infection. When using sequential estrogen-progesterone therapy to treat retained products of conception, withdrawal bleeding occurs after drug discontinuation, which promotes the expulsion of intrauterine remnants. Qin Huandi's study^[15] proposed that the success rate of estrogen-progesterone therapy decreases as the maximum diameter of the lesion increases. When the diameter of the remnant exceeds 2.5 cm, the success rate of drug treatment is less than 50%.

With the development of medical technology, the surgical treatment of retained products of pregnancy has become more diversified. Traditional curettage is simple to operate and has a clear therapeutic effect. It can expel the retained products of pregnancy from the uterus in a short time and solve the symptoms of vaginal bleeding. Moreover, curettage has low requirements for surgical equipment, is easy to carry out, and is relatively inexpensive. Therefore, it is widely carried out in primary hospitals and is still the main treatment method. However, due to its blind nature, this treatment method is prone to incomplete curettage, requiring repeated curettage, or excessive curettage, which damages the basal layer of the endometrium, leading to intrauterine adhesions and subsequent abnormal implantation of the placenta. At present, hysteroscopic surgery is considered the preferred method for treating retained products of pregnancy^[16]. It greatly reduces the blindness of intrauterine operation, reduces damage to the endometrium, and thus reduces the risk of intrauterine adhesions.

Hysteroscopic electrosurgical resection of pregnancy has a short operation time and less intraoperative bleeding. Direct visualization during the operation can avoid extensive curettage of the endometrium and significantly reduce complications such as incomplete curettage. For patients with uterine malformations, it can avoid blind curettage that misses part of the uterine cavity and leads to incomplete curettage, and can also treat uterine malformations simultaneously under hysteroscopy. However, the electrosurgical ring brings thermal radiation damage during treatment, which can easily damage the surrounding endometrial tissue, increase the risk of intrauterine adhesions, and in severe cases, damage the basement membrane or even the deep myometrium, leading to abnormal placental implantation in subsequent pregnancies [17].

Hysteroscopic cold knife removal of pregnancy tissue has no electrothermal damage, which is beneficial to protect the endometrium and reduce the risk of intrauterine adhesions and infertility after curettage. It is increasingly widely recognized [18]. Literature [19] compared the treatment of intrauterine diseases with electrocautery system and cold knife system and found that the latter reduced the incidence of intrauterine adhesions by 90% after surgery and could effectively avoid damage to the surrounding endometrial tissue by electroradiation. At present, the application of giant cold knife instruments is becoming more and more widespread. For example, the 4mm (i.e. 12 Fr) spoon forceps can directly remove residual tissue under vision, which has a great advantage over traditional micro forceps. The hysteroscopic shaving system uses a blunt head and side window operation to remove lesion fragments while removing lesions, avoiding repeated entry and exit from the uterine cavity. Its operation time is significantly shorter than that of the electrocautery group,

and the incidence of serious complications such as uterine perforation and massive bleeding is significantly reduced. At the same time, it avoids electrothermal radiation damage and significantly reduces intrauterine adhesions. However, it is important to emphasize the correct use method when using it, especially to avoid damage caused by excessive cutting of the endometrium.

In summary, hysteroscopic surgery is the most effective treatment for patients with large retained products of conception. However, due to the large size of the lesion, especially in cases of a large uterus, high serum HCG levels, and rich blood supply, the likelihood of needing repeat or even multiple curettage procedures increases, raising the risk of infection and endometrial damage. This not only increases costs but also leads to intrauterine adhesions and infertility. For these patients, appropriate drug treatment or expectant management followed by hysteroscopic surgery may be a wise choice and warrants further clinical research. Drug treatment and expectant management are also effective and safe under certain conditions for managing retained products of conception. Previous studies have shown that expectant management can allow some patients to expel the retained products of conception spontaneously, avoiding curettage; when curettage is performed 1-3 months after termination of pregnancy, serum HCG levels drop to low levels, reducing the difficulty of hysteroscopic surgery, intraoperative risks, and the likelihood of repeat surgery, as well as the incidence of postoperative intrauterine adhesions. Therefore, we propose the following scientific hypothesis: for patients with retained products of conception, in the absence of infection and active bleeding, expectant management should be maintained until the appropriate surgical time, thereby reducing the likelihood of repeat surgery and protecting the endometrium. To verify this scientific hypothesis, we designed a prospective, observational, multicenter, real-world study. The study subjects were patients with retained products of conception without bleeding or infection. Under the guidance of the physicians in the treatment group and with full informed consent, patients were selected according to their wishes to either the active surgery group (control group) or the expectant management group (study group). The diagnosis and treatment procedures were standardized, and detailed clinical data were collected to explore the optimal treatment strategy for retained products of conception, especially the best treatment plan for the protection of fertility.

II. Research Objectives

This study aims to explore optimized treatment strategies for retained products of pregnancy in the uterine cavity. In the absence of infection and active bleeding, a prospective observational study with medication-assisted expectant management until the appropriate surgical time can reduce the number of curettage procedures and endometrial damage, decrease the incidence of intrauterine adhesions, and thus protect fertility compared to aggressive surgical treatment.

III. Project Overview

Leveraging the advantageous resources of the Hunan Provincial Medical Association's Hysteroscopy Group, the Hunan Provincial

Alliance for the Prevention and Treatment of Major Obstetric and Gynecological Diseases (already approved), the Hunan Provincial Demonstration Base for Minimally Invasive Hysteroscopic and Laparoscopic Techniques, and the Hunan Provincial Quality Control Center for Gynecological Disease Diagnosis and Treatment, and under the guidance of the Gynecological Intelligent Diagnosis and Treatment Branch of the National Health Industry Enterprise Management Association, this multicenter prospective observational real-world study, led by the Third Xiangya Hospital of Central South University, selected 13 or more provincial and municipal hospitals willing to participate to explore the optimal surgical timing for retained products of conception. For patients meeting the inclusion and exclusion criteria, with the guidance of the treatment team physicians and full informed consent, patients were given the option of either **active surgery or expectant management until a certain timeframe, with surgery performed only when necessary**. Detailed clinical data (including follow-up clinical data) were collected. This study did not intervene in the study subjects, nor did it add any additional examinations or tests to the patients. All procedures were conducted according to standard medical practice, with only the pre-designed treatment plan and data collection. After treatment, patients were divided into active surgery and expectant management groups based on their treatment plans, and data were statistically analyzed. Before the study began, standardized training was provided in diagnosis and treatment, especially in the standardization of ultrasound measurement of relevant indicators; expectant management, perioperative care, surgical record keeping, and postoperative follow-up all followed the corresponding standardized diagnosis and treatment protocols.

IV. Research Design

1. Research Subjects

who were diagnosed with retained products of pregnancy by ultrasound at outpatient clinics of various research units between June 2022 and June 2024, and who met the inclusion criteria but did not meet the exclusion criteria, were all enrolled consecutively.

Inclusion criteria: age 18-45 years, clinical diagnosis of retained products of conception, and ultrasound showing a lesion with a maximum diameter ≥ 0.5 cm.

Exclusion criteria: 1) Active bleeding requiring immediate surgical intervention; 2) Significant infection; 3) Severe organ dysfunction, including coagulation disorders.

Note: Patients with cervical tissue impacted in the cervical canal who have undergone clamping treatment and do not meet the exclusion

criteria can be included in this study;

2. Grouping

Because there is currently no unified treatment plan for retained products of pregnancy in uterus, the timing of active surgical evacuation versus expectant management until the planned surgery remains controversial, and the optimal timing for surgical evacuation is not uniform. In clinical practice, physicians, based on fully informed consent, choose active surgical treatment or expectant management according to the patient's wishes, and perform surgery when necessary. This study does not interfere with patient treatment; it only designs and collects relevant data in advance. No additional examinations or tests are performed on patients during the study process, and all procedures are conducted according to standard clinical practice. After treatment, patients are divided into an active surgical group and an expectant management group based on their chosen treatment plan, and data are statistically analyzed.

3. Sample size and allocation

The sample size was determined based on the incidence of intrauterine adhesions, the primary outcome measure. According to previous research results, the intrauterine adhesion rate in the expected group was 5.38%, and the intrauterine adhesion rate in the patients undergoing active surgery was 14.29%. The Type I error was 0.05, the power was 90%, and the sample size was calculated using PASS to obtain a total of 460 cases. Based on a 20% follow-up dropout rate, the sample size was calculated to be 576 cases. It is expected that 600 cases will be included, with 120 cases from the lead institution and an average of 40 cases from the other 12 research institutions.

4. Research Process

4.1 Pre-hospitalization treatment

4.1.1 Active surgery group: Patients were admitted directly after enrollment and were scheduled to undergo hysteroscopic removal of pregnancy tissue.

4.1.2 Expectant Treatment Group

1) In the outpatient clinic, complete routine examinations of vaginal secretions, blood β -HCG, complete blood count, CRP, procalcitonin (optional), chlamydia and gonococcus, and other infection indicators. If the 4D color ultrasound indicates placenta accreta or retained products of conception in special locations such as the uterine horn or cesarean section incision site (CSP), and if necessary (especially when CSP or interstitial retained products of conception cannot be ruled out), complete a pelvic MRI plain scan with contrast. At the same time, complete liver and kidney function tests and coagulation function tests.

2) For patients without contraindications, administer 2mg of Progynova twice daily (or a similar dose of Estradiol) until postoperatively (generally, continue using Progynova for 2-4 weeks postoperatively with progesterone withdrawal bleeding); then

discontinue oral administration of Leonurus japonicus granules or Acanthopanax senticosus capsules for 2 weeks.

4D color Doppler ultrasound of the uterus and adnexa every 2-3 weeks ; until **the predetermined surgical timing is reached** : 1) Blood β -HCG <50mmol / L; 2) Ultrasound measurement of the length from the internal cervical os to the fundus \leq 6cm; 3) At least 4 weeks between the previous surgery; 4) Color Doppler ultrasound showing blood flow grade 1-3 at the pregnancy tissue and attachment site . This predetermined surgical timing is proposed based on our hospital's summary of previous patient data and literature analysis. Research hospitals can adjust the surgical timing parameters according to clinical experience. Patients who reach the predetermined surgical timing will be hospitalized, undergo relevant examinations, and undergo hysteroscopic removal of the pregnancy tissue (hysteroscopic surgery using a large cold knife instrument is recommended ; refer to the surgical video).

4) If massive bleeding (more than twice the amount of menstrual flow) occurs during the expected treatment, emergency hospitalization should be performed, and a detailed record should be kept (including the bleeding situation, whether interventional treatment was performed, and the surgical curettage). If infection occurs during the expected treatment, emergency hospitalization should be performed, and after aggressive anti-infection treatment, a curettage procedure should be performed as appropriate (generally, curettage should not be performed), and a detailed record should be kept (including the infection situation and the surgical curettage). Both of the above situations should be reported as adverse events.

If, during the waiting period, the pregnancy tissue is expelled and the remaining tissue is less than 0.5 cm in diameter, an artificial cycle will be performed. After the next menstrual period, a follow-up ultrasound and HCG test will be conducted to determine whether further surgery is needed.

The expectant treatment group can be hospitalized at any time if the patient's condition is relatively complex or the risk of bleeding and infection is high, after the patient gives informed consent, based on the physician's assessment.

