4.2.3 Postoperative management

Prevention of intrauterine adhesions: 1) **Inject sodium hyaluronate gel (Gongankang or Yishukang)** into the uterine cavity according to the uterine depth (2-3 ml for a uterine depth of 7 or 8 cm , 5 ml for a uterine depth of 10 cm). 2) If necessary, leave the uterine balloon in place for 48-72 hours and remove it. If there are adhesions in the lower segment of the uterine cavity, part of the internal cervical os, or complete adhesions, handle them according to the intraoperative situation; adjust the amount of water injected into the balloon according to the uterine depth (3 ml for a uterine depth of 7-8 cm, 3.5 ml for a uterine depth of 9 cm, and 4 ml for a uterine depth of 10 cm) . 3) If there are no contraindications, administer 2 mg BID of estradiol valerate (or an equivalent dose of estradiol) orally for 21-28 days postoperatively. (For patients with serum β -HCG levels not typically associated with pregnancy, oral administration until 21 days post-surgery; for patients with β -HCG levels above 100 mmol /L, oral administration until 28 days post-surgery). For the following 6 days, add progesterone (or dydrogesterone) 200 mg orally before bedtime. Continue for a total of two menstrual cycles. Adjustments may be made based on the condition of patients with other intrauterine diseases.

Treatment to promote uterine contraction: routine intravenous administration of uterine contraction agents (ostomycin is routinely used, and ergonovine may be used if necessary) for 48 hours after surgery; oral administration of uterine contraction-promoting drugs (such as *Acanthopanax senticosus* capsules, etc.) for 2 weeks.

Infection prevention: If there are signs of infection or high-risk factors for infection, antibiotics may be used as appropriate, and the type of antibiotic, route of administration, dosage, frequency and duration of administration should be recorded accurately.

Pathological examination: The pregnancy tissue removed during the operation is routinely sent for pathological examination. If endometritis is suspected, endometrial tissue can be sent for immunohistochemical examination of CD138. CNVs can be performed if genetic testing is required.

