4.3 Data collection process

4.3.1 Outpatient data collection: The patient's first outpatient visit data and each outpatient follow-up visit data include main symptoms, blood β -HCG, ultrasound and infection-related indicators.

4.3.2 Data collection for inpatient surgery includes: preoperative symptoms; serum β -HCG, ultrasound and infection-related indicators; surgical data; and postoperative medication.

4.3.3 Follow-up after surgical treatment:

(1) If the ultrasound examination 3 days after the operation shows no pregnancy residue or the diameter of the residue is less than 0.5cm, follow up by phone or WeChat 1 month later to ensure that the patient's menstruation is over and to have a follow-up examination of β -HCG, ultrasound and other indicators at the outpatient clinic to determine whether the treatment has ended.

(2) If the ultrasound examination on the 3rd day after surgery shows that the

diameter of the retained pregnancy tissue is greater than 0.5cm, follow up by phone or WeChat half a month later to ensure that the patient goes to the outpatient clinic on schedule for β -HCG, ultrasound and infection indicators, and to determine the subsequent treatment plan.

4.3.4 Data collection after treatment: Menstrual flow, ultrasound findings of intrauterine adhesions, and endometrial thickness were collected during outpatient follow-up examinations three times after the end of treatment.

4.3.5 Data collection on reproductive outcomes: For patients who wish to have children, follow-up by telephone will continue every 3 months. If the patient has not become pregnant after 1 year of follow-up, the follow-up will be terminated. If the patient becomes pregnant within 1 year, follow-up will continue until the pregnancy is terminated, including whether there is spontaneous abortion, premature birth, full-term birth, stillbirth, or stillbirth.

5. Data Collection

5.1 General information: age, parity, number of previous intrauterine procedures, history of intrauterine adhesions, occupation, and education level.

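### The groups differ in pre-operative oestrogen as well as surgical timing, and the data lists do not name that exposure, so a lower adhesion rate could not be credited to delay alone

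*Protocol*

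**What the plan says.** **Treatment before surgery.** Section 4.1.2, item 2, tells sites, for expectant patients without contraindications, to "administer 2mg of Progynova twice daily (or a similar dose of Estradiol) until postoperatively", so the drug is carried through the wait until after the operation. For the active surgery group, 4.1.1 says only: "Patients were admitted directly after enrollment and were scheduled to undergo hysteroscopic removal of pregnancy tissue". No pre-operative oestrogen is described there.

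**Treatment after surgery.** Section 4.2.3, under its adhesion-prevention measures and without limiting this to one group, says to "administer 2 mg BID of estradiol valerate (or an equivalent dose of estradiol) orally for 21-28 days postoperatively".

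**What is claimed.** The hypothesis at the end of the Background is that "expectant management should be maintained until the appropriate surgical time, thereby reducing the likelihood of repeat surgery and protecting the endometrium". It names no drug. The Project Overview gives the aim as exploring the optimal timing of surgery. The Research Objectives, by contrast, describe the waiting strategy as assisted by medication.

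**Non-intervention.** The Project Overview states: "This study did not intervene in the study subjects". The Grouping section says much the same.

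**Data.** Section 4.3.1 lists symptoms, β-HCG, ultrasound and infection indicators at outpatient visits. Section 5.2 lists blood count, β-HCG, CRP and ultrasound at each expectant follow-up. The only medication entry is in 4.3.2, which ends its inpatient list with "surgical data; and postoperative medication".

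**Primary outcome.** Section 6.1 names the incidence of intrauterine adhesions.

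**The concern.** The two groups are set up to differ in two respects at once: when surgery happens, and whether oestrogen is taken beforehand. The protocol itself connects the second to the primary outcome. It lists the same drug and dose among the adhesion-prevention measures, and its Background credits oestrogen with repairing the endometrium.

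If the expectant group has fewer adhesions, the hypothesis as worded would lead the authors to report that waiting for the right moment protects the endometrium. The result would equally fit a benefit of the drug, of the delay, or of both. A centre that adopted the delay without the hormone would be relying on evidence the study had not produced.

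A later analysis plan can reword an estimand, but it cannot recover an exposure that was never recorded.

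**Working it through.** **1. The plan's own figure.** Inputs from the sample-size section: 14.29% (active), 5.38% (expectant), Type I error 0.05, power 90%, 20% dropout. Assumed: two-sided test, equal groups, unpooled normal approximation.

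n per group = (1.960 + 1.282)² × [0.1429 × 0.8571 + 0.0538 × 0.9462] / (0.1429 − 0.0538)² = 229.5, so 230 per group and 460 in total, as stated. Dropout: 230 / 0.80 = 287.5, so 288 per group and 576 in total, as stated. The sample size is not in question. The planned difference is 14.29 − 5.38 = 8.91 percentage points.

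**2. Exposure by group, as written.**

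| | Expectant | Active surgery |
|---|---|---|
| Surgery | after a wait, when the timing criteria are met | on direct admission |
| Oestrogen before surgery | yes, unless contraindicated (4.1.2) | none described (4.1.1) |
| Oestrogen after surgery | yes (4.1.2, 4.2.3) | yes (4.2.3) |

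The first two rows differ together.

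**3. What one contrast can show.** Write the observed difference in adhesion rates as D = (effect of delay) + (effect of pre-operative oestrogen) + (any interaction). The study estimates D. The documents give no figure for oestrogen alone, so no part of the 8.91 points can be allotted to it. D answers whether one strategy does better than the other. It does not answer whether delay alone does.

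**4. Whether the listed data could help.** Going through 4.3.1, 4.3.2 and 5.1 to 5.7, no item records whether oestrogen was given before surgery, or the product, dose, dates or reason for withholding it. Yet exposure will vary. Women with contraindications are exempt, a similar estradiol dose may be substituted, and sites may adjust the timing parameters (4.1.2). Section 4.2.3 also returns women with residue above 0.5 cm after surgery to the expectant process, which may bring active-group women into the same pathway.

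**5. Whether recording it would separate drug from delay.** It would not. With the planned numbers, adhesions expected among evaluable expectant women are 230 × 0.0538 = 12.4, about 12. The women without oestrogen would be mainly those with contraindications, who differ in other ways. A split of about 12 events on that basis would be sparse and confounded. Recording the exposure describes the strategy actually delivered.

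**The case against.** The strongest reply is that the study compares strategies and says so. The Research Objectives name medication-assisted waiting. The Background, although it says that non-"surgical treatment mainly includes expectant management and drug treatment", also describes adding hormones to expectant management to improve its results. Under that reading oestrogen belongs to the strategy and does not confound it. This stands for the stated objective. It does not rescue the hypothesis or the aim of finding the best surgical timing, both of which omit the drug.

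A reader might infer that the non-intervention statement presents the expectant group as drug-free. It does not. In context it means that patient and physician choose the treatment, no tests are added and care follows usual practice. It still sits uneasily beside an instruction to administer a drug, so the passages need reconciling.

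A reader might also try to size the imbalance as 30 to 90 days of waiting added to two postoperative courses of 21 to 28 days: (30 + 56)/56 = 1.54 up to (90 + 42)/42 = 3.14 times the active group's exposure. The document does not support this:

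- The one to three months in the Background run from termination of pregnancy, not from the start of oestrogen.
- Section 4.1.2 gives 2 to 4 postoperative weeks for the expectant group. On that text, even a 30-day wait could give (30 + 14)/56 = 0.79.
- Women who expel the tissue may have no surgery; in the retrospective cohort cited in the Background, 34 of 44 (77%) did not.

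No ratio can be defended.

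Finally, the case report form is not shown and may hold a medication field. That is possible, but the protocol's own data lists do not require one.

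**Conclusion.** The point holds as one of attribution and data capture. By design the groups differ in pre-operative oestrogen as well as in timing. The drug is one the protocol lists for preventing the primary outcome, and the data lists name only postoperative medication. A lower adhesion rate would support the medication-assisted delayed strategy; it could not be assigned to delay alone.

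The size of the drug's contribution, from none to all of the planned 8.91 points, cannot be determined from the document. The conclusion does not depend on that size. It assumes that 4.1.1 is complete in describing no pre-operative oestrogen for the active group, and that the case report form follows the protocol's lists.

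It would go too far to say that the strategy comparison is invalid, that the expectant group is presented throughout as untreated, or that no medication is recorded. The protocol should be corrected because this changes what the study may conclude.

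**What to change.** 1. Reconcile the hypothesis in the Background, the timing aim in the Project Overview and the Grouping text with the Research Objectives and 4.1.2. The hypothesis, group label and conclusion should describe a comparison of strategies, medication-assisted delayed surgery versus active surgery, with no claim for timing alone.
2. Reconcile the non-intervention statements in the Project Overview and Grouping with the drug instruction in 4.1.2, for example by stating what the study does and does not determine about care.
3. Add pre-operative hormone exposure to 4.3.1 and 5.2: given or not, product, dose, start and stop dates, and reason if not given. Report it descriptively. Do not present a split of the outcome by oestrogen use as separating drug from delay.

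The cost is some rewording, a few data fields, one descriptive table and a narrower claim. Women already followed without these fields would need the information taken from their records where it exists. No change to the regimen is proposed.
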